##### 5.5.4.2 Positive Predictive Value (PPV) Adjusted Analysis

A PPV-adjusted risk estimate will also be calculated using the PPVs from the medical record review process (see Section 6). While the IRRs are directly obtained from the primary claims-based analysis, they might not be truly representative of the underlying stroke outcomes risk given certain claims-identified cases may not be true cases during the observation period. PPV adjusted results may be reported subsequent to primary analysis results.

### 5.5.5 Secondary Analysis I: Temporal Scan

To identify clusters of increased stroke risk within the 1-90-day period after bivalent booster vaccination, we will conduct a retrospective temporal scan. We will use SaTScan to perform the analysis. The temporal scan will only be conducted for analyses of interest, to be determined after completion of the SCCS analyses.

In order to identify clusters of meaningful specificity and size, we will set the maximum cluster size to be 50% of the observation period (45 days) and the minimum window length to 3 days. The unit of time aggregation will also be 3 days.

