### 2.2 Secondary Objectives

The secondary objectives of this study are to:

- I. Conduct a temporal scan to identify clusters of stroke outcomes after exposure to the Pfizer-BioNTech COVID-19 Vaccine, Bivalent and Moderna COVID-19 Vaccine, Bivalent COVID-19 mRNA bivalent booster doses (by brand) among Medicare beneficiaries age 65+.
- II. Evaluate the independent risk of stroke outcomes (as defined in Section 4.3) following exposure to a high-dose or adjuvanted influenza vaccine (without concomitant administration of a bivalent booster) among Medicare beneficiaries age 65+, if power allows. This analysis will only be conducted on outcomes for which an increased risk of any stroke outcome following concomitant bivalent booster and influenza vaccination is identified.

SCCS analyses can be sensitive to the specification of intervals (risk and control). The temporal scan analysis will identify clusters of stroke outcomes for further consideration and evaluation. We will use the temporal scan analysis to validate our risk interval choices during the observation period.

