### 5.4.2 Risk Window

The risk interval is defined as the time during which risk of a stroke outcome is hypothesized to be related to vaccination based on biological plausibility and clinical input (Table 2). The selected risk intervals for all stroke outcomes are days 1-21 and days 22-42. The 1-21 day risk interval was selected to align with the definition of stroke as used by the CDC in their RCA. The 22-42 day risk interval is selected to assess any difference in risk during this period, and to avoid any biases in risk estimates that may arise from a carryover effect from the vaccine exposure into the control interval. Implementing a split window addresses concerns that risk of the outcomes may not be constant throughout the risk period. Risk intervals will not be split further in an effort to preserve statistical power.

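### The temporal scan is meant to validate the risk windows for every brand and outcome, but Section 5.5.5 limits it to analyses chosen, without a stated criterion, after the SCCS results are known

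*Protocol*

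**What the plan says.** Section 2.2 of the protocol lists the scan as secondary objective I: "Conduct a temporal scan to identify clusters of stroke outcomes after exposure to the Pfizer-BioNTech COVID-19 Vaccine", and likewise for the Moderna product, by brand, in beneficiaries aged 65 and over. No condition is attached. Secondary objective II, the influenza-vaccine analysis, carries two explicit conditions (adequate power and a raised risk in the concomitant group), so the authors state a condition where they intend one. The same section notes that SCCS results can depend on how risk and control intervals are set, and continues: "We will use the temporal scan analysis to validate our risk interval choices during the observation period".

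Section 5.4.2 fixes those intervals: "The selected risk intervals for all stroke outcomes are days 1-21 and days 22-42". Under Section 5.4.3 the rest of follow-up, to day 90 at most, is control time.

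Section 5.5.5 describes the scan: "To identify clusters of increased stroke risk within the 1-90-day period after bivalent booster vaccination, we will conduct a retrospective temporal scan". Its settings are also fixed: "we will set the maximum cluster size to be 50% of the observation period (45 days) and the minimum window length to 3 days", and "The unit of time aggregation will also be 3 days". The section then restricts its use: "The temporal scan will only be conducted for analyses of interest, to be determined after completion of the SCCS analyses". It does not say what makes an analysis one of interest, and it gives no significance level for the scan and no allowance for the selection.

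**The concern.** A check on the risk windows should not depend on the results obtained with those windows. Excess cases in days 43-90 raise the control rate and pull both IRRs down. A cluster that crosses day 42 raises numerator and denominator together. Either way, a misplaced window tends to appear as a null, diluted or apparently protective IRR. In a safety study these are the results least likely to prompt a further look, yet they are where the scan has most to offer.

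The opposite case matters too. If a scan is run because the SCCS was significant, it uses the same excess of cases again. A reader who sees only the scans that were run could take a positive one as separate confirmation.

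**Working it through.** **The plan's own figure.** Maximum cluster length: 0.50 × 90 = 45 days, as stated. With 3-day aggregation there are 90 / 3 = 30 bins, and windows of 1 to 15 bins give 30 + 29 + … + 16 = 345 candidate windows.

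**Inputs from the protocol.** Risk windows are days 1-21 and 22-42, with control days 43-90 (48 days) under full follow-up. SCCS significance is two-sided at 0.05 for each window (Section 5.5.2.1). There are four outcomes by two brands (Section 4.3), so 8 primary analyses.

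**Assumptions not in the protocol.** 600 cases per analysis, complete follow-up to day 90, no Farrington adjustment, and two possible selection rules: (a) any two-sided significant IRR in either window; (b) a significantly raised IRR in either window. The protocol states neither rule. They bracket a plausible results-driven choice.

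**Expected IRRs under a misplaced window.**

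- 1.5-fold cluster on days 43-60 (18 control days): control rate = 1 + 0.5 × 18/48 = 1.1875; both IRRs = 1 / 1.1875 = 0.84.
- 1.6-fold cluster on days 37-51 (6 days in the second risk window, 9 in control): second-window rate = 1 + 0.6 × 6/21 = 1.171; control rate = 1 + 0.6 × 9/48 = 1.1125; IRR = 1.171 / 1.1125 = 1.05 for days 22-42 and 1 / 1.1125 = 0.90 for days 1-21.

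In both cases a real excess yields IRRs at or below about 1.05.

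**Simulation.** Cases are multinomial over the 30 bins. The scan statistic is the maximum over the 345 windows of x·ln(x/e) + (N − x)·ln[(N − x)/(N − e)] where x > e, with e = N × (window length / 90). Its 5% critical value is simulated under a uniform null. The SCCS is approximated by z = ln[(a/21)/(d/48)] / √(1/a + 1/d), where a is the case count in a risk window and d the count in control time, with significance at 1.96.

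Probability that the scan is run and finds the cluster, 600 cases:

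| True pattern | Always run | After any significant IRR | After a raised IRR |
|---|---|---|---|
| 1.5-fold, days 43-60 | 91% | 55% | about 0% |
| 1.6-fold, days 37-51 | 95% | 24% | 8% |

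**Other case counts.** For a 1.5-fold cluster on days 43-54 with 300, 1,000 and 3,000 cases, detection is 43%, 96% and 100% if always run, 14%, 48% and 89% after any significant IRR, and 0.4% or less after a raised IRR. For a 1.5-fold cluster across the day 21/22 cut (days 16-27), detection is 41%, 96% and 100% if always run, and 20%, 58% and 95% after either rule.

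**No effect.** An unselected scan is positive in about 5% of data sets. Among data sets with a significant SCCS result under either rule, it is positive in about 20%, and this hardly changes between 300 and 3,000 cases. The rules select about 9% (any significant IRR) and 5% (raised IRR) of null analyses, so the joint probability of selection and a positive scan is about 0.09 × 0.19 ≈ 2% and 0.05 × 0.21 ≈ 1%.

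**The case against.** The strongest reply is that the harmful selection rule is assumed. Section 5.5.5 says when the choice is made, not that it depends on significance. Null or protective-looking results, or all primary analyses, could be judged of interest. That is correct, and it is why the figures are conditional. What stands against it is that the protocol itself places the choice after the results and leaves it open, while Section 2.2 promises the scan without condition. This is a stated rule that conflicts with a stated objective, not a detail that a protocol would simply leave to the SAP.

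A reader might infer three stronger things that the text does not support.

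- That the scan cannot find a window the SCCS missed. Where it is run it covers all of days 1-90 and can find clusters outside or across the risk windows. The loss is confined to analyses that are not selected.
- That scan p-values are inflated as a matter of course. This holds only if selection follows the SCCS results. Even then about four in five chance SCCS findings would not be echoed by the scan, and the joint error is 1-2%, below the nominal 5%. Section 2.2 also presents clusters as matters for further evaluation, not as confirmatory tests.
- That the choice of risk windows is left unprotected. Section 5.4.2 rests it on biological plausibility, clinical input and alignment with the CDC analysis, and adds days 22-42 partly to deal with carryover. The scan is an additional check.

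The near-zero detection also belongs only to the raised-IRR rule. A cluster in control time can make both IRRs significantly low, which an alert analyst might pursue; the two-sided column allows for this. The days 37-51 example is an unfavourable one, because the excess nearly cancels between risk and control time.

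**Conclusion.** The point holds in a limited form. Sections 2.2 and 5.5.5 disagree on the scope of the scan, and the restriction weakens the one analysis that the protocol names for validating its risk intervals. If selection follows the SCCS results, detection of a misplaced window can fall substantially even under the more generous rule: from 91% to 55%, or from 95% to 24%, in the two 600-case examples. A positive scan in a selected analysis is then weaker evidence than its nominal level suggests. The sizes rest on assumed case counts, full follow-up, an unadjusted SCCS and assumed selection rules. With 3,000 cases and the two-sided rule much of the loss disappears (89% against 100% for days 43-54). The scan is secondary, so this should be corrected but does not call the primary analysis into question.

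**What to change.** Replace the restricting sentence in Section 5.5.5 with:

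> The scan will be run for all eight primary brand-by-outcome combinations (2 brands × 4 outcomes), whatever the SCCS result; scan p-values are exploratory and will be interpreted in light of the eight scans performed. Any further scans, for example in subgroups, will be labelled post hoc.

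This brings Section 5.5.5 into line with Section 2.2 and removes the dependence on the SCCS results. The cost is one sentence and at most eight SaTScan runs on data already prepared. The drawback is more opportunity for a chance cluster: with eight scans at 5%, the probability of at least one is 1 − 0.95^8 = 34% if they were independent. That is illustrative, since the outcomes overlap. The exploratory label deals with it; a multiplicity adjustment across the eight would be the alternative.

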### 5.5.6 Secondary Analysis II: Influenza Vaccines

If we observe a risk of any stroke outcome in the concomitant vaccinated subgroup, we will conduct a secondary SCCS analysis to evaluate the risk of that stroke outcome following high-dose or adjuvanted influenza vaccination (without concomitant bivalent booster vaccination). Similar to the primary analysis, this analysis will compare the stroke outcomes rates in the risk and control intervals using a conditional Poisson regression model. A Farrington-adjusted SCCS model will be implemented that adjusts for the reduced observation time that can occur from the occurrence of an outcome.

### 5.5.7 Follow-Up Analysis I: Nursing Home Residents

The specifications for the statistical analysis portion of the secondary analysis on nursing home residents will be consistent with the primary analysis (Section 5.5.2).

### 5.5.8 Follow-Up Analysis II: Alternate Setting Definitions

To evaluate the performance of our outcome setting definitions and to align algorithms to those of the CDC, we will conduct an exploratory SCCS analysis for the NHS, HS, and NHS/TIA outcomes. The specifications for the statistical analysis portion of the exploratory analysis will be consistent with the primary analysis (Section 5.5.2).

## 5.6 Statistical Power and Sample Size Calculations

To ensure sufficient sample size, a power analysis will be conducted to evaluate the minimum detectable IRR for each of the stroke outcomes following COVID-19 bivalent booster vaccination, at 80% power and a two-sided alpha of 0.05. A minimum detectable IRR will be calculated at various data cutoff dates for the study, and the study cutoff data date will be determined based on an assessment of minimum risk detection at varied timeframes. A 90% threshold for data completeness is required at the specified data cutoff date to reduce differences in data accrual and the likelihood of observing events during risk relative to control intervals. Minimum detectable IRRs will be benchmarked against a comparable stroke outcomes risk estimate following either COVID-19 bivalent booster or third/monovalent booster doses present in the literature, to ensure sufficient sample size to detect the hypothesized IRR.

## 6 Medical Record Review

During the course of the study, a sample of medical records for each stroke outcome will be retrieved and undergo an adjudication process to assign cases identified in claims data as true cases, non-cases, and potentially indeterminate. We will sample to attain:

- 30 Cases of HS
- 30 Cases of NHS
- 30 Cases of TIA

A clinical case definition based on clinical input from subject matter experts will be used for each stroke outcome. The study will identify appropriate clinical reviewers to review the redacted medical records and abstracted data to recommend expert case designations.

If we conduct an influenza vaccine only analysis, a sample of medical records for the relevant stroke outcomes following influenza vaccination will also be retrieved and undergo a similar adjudication process.

## 7 Ethical Evaluation

This surveillance activity is conducted as part of the FDA CBER Initiative under the FDA Amendments Act of 2007. This current study performs analysis using Medicare administrative claims data. The study will not involve personal health information; no intervention will be conducted on study participants; data used in this study will be de-identified and anonymized before its use.

Using Medicare data for this surveillance activity is permitted under the HIPAA Privacy Rule for public health practice without individual authorization. Furthermore, public health surveillance activities including this study are not subject to the Common Rule as verified in the Office of Human Research Protections correspondence. Therefore, this study as a public health surveillance activity is exempt from an IRB review and approval. In addition, our study practices will be performed in accordance with the Declaration of Helsinki guidelines.

## 8 Quality Assurance and Control

The analyses described in this protocol will be conducted using a well-characterized database, the CMS Medicare database, in which OBPV has previously conducted numerous epidemiologic studies. For the current study, the team has performed quality control measures in the database such as executing checks examining the validity of claims data variables, stability of enrollment and health outcome trends, and consistency with population selection criteria for the database, if any. In addition, the team has validated codes for identifying individuals who received a COVID-19 vaccination and those who have been diagnosed with a stroke outcome.

Data quality is continuously monitored with every update from the study database to ensure insurance claims representing vaccinations and stroke outcomes are captured accurately. As an overall check, the total number of claims newly observed in each data cut will be counted, stratified by care setting and

HHS region. If substantial increases or decreases in the rate of claims accrual relative to previous cuts are observed, steps will be implemented to trace the potential causes of the discrepancy, such as by examining regions with accrual different from the national average, examining whether the data cut spans holidays that may reduce service utilization, or identifying providers whose claims submission patterns have changed. The study will also conduct more specific checks on the health care encounters occurring in care settings similar to COVID-19 vaccination or stroke outcomes, such as other vaccinations as negative control exposures or hospitalization for external injuries as negative control outcomes. Well-established and validated software such as SAS version 9.4, Stata version 17, R version 4.1.2, and SaTScan will be used for statistical analyses.

## A Appendix

**Table A. ICD-10 Codes Which Indicate Onset Date Adjustment or Exclusion for Outcomes of Interest**

Outcome	Adjust onset date if observed in the 1 day prior to outcome (in all settings)	Exclusions for Prevalence (in all settings)	Exclusions – other known causes (in all settings)
Hemorrhagic Stroke (HS)	I63.9, R51*, R47*, R29.810, R53.1, R42*, R41.82, R40.4, H53.13*, H53.9, G81.9*	If occurs in the 365 window prior to outcome I69*, Z86.73	If in last 30 days prior to outcome U07.1 If in last 1 day prior to outcome S06* If same day as outcome S06*, Physical Trauma Code
Non-Hemorrhagic Stroke (NHS)	Z92.82, R51*, R47*, R29.810, R53.1, R42, R41.82, R40.4, G81.9*, H53.9, H53.13*	If occurs in the 365 window prior to outcome I69*, Z86.73, I48*, D57*, D68.5*	If in last 30 days prior to outcome U07.1 If in last 28 days prior to outcome I21* If in last 1 day prior to outcome S15*, 174* In same day as outcome S15*, I74*, Physical Trauma Code

Outcome	Adjust onset date if observed in the 1 day prior to outcome (in all settings)	Exclusions for Prevalence (in all settings)	Exclusions – other known causes (in all settings)
Non-hemorrhagic stroke or Transient Ischemic Attacks (NHS / TIA)	Z92.82, R51*, R47*, R29.810, R53.1, R42, R41.82, R40.4, G81.9*, H53.9, H53.13*	If occurs in the 365 window prior to outcome I69*, Z86.73, I48*, D57*, D68.5*	If in last 30 days prior to outcome U07.1 If in last 28 days prior to outcome I21* If in last 1 day prior to outcome S15*, I74* In same day as outcome S15*, I74*, Physical Trauma Code
Transient Ischemic Attacks (TIA)	R51*, R47*, R29.810, R53.1, R42, R41.82, R40.4, G81.9*, H53.9, H53.13*	If occurs in the 365 window prior to outcome I69*, Z86.73, I48*, D57*, D68.5*	If in last 30 days prior to outcome U07.1 If in last 28 days prior to outcome I21* If in last 1 day prior to outcome S15* In same day as outcome S15*, Physical Trauma Code
